Older obese adults suffer disproportionately from walking mobility limitations. Sedentary, obese older adults are at an increased risk for having or developing difficulties with mobility. These individuals are often excluded from studies due to their advanced mobility limitations. A number of studies have compared the effects of weight loss alone, exercise alone, or weight loss in combination with exercise on functional performance in older adults, but none of the studies have specifically targeted subjects who use walking assistive devices. The purpose of this study is to test the effects of a 3 month multi-modal balance intervention (MMBI) with a nutrition program with optional retention till 24 months on fitness, functional performance, mobility, and muscle mass. The results of this study will lead to new and more effective interventions that could reduce disability, fall risk, injury-related hospitalization and death in older Veterans.

ID: VIEW4E02805CF7000
Name: v2_Lay Summary

Justification, Objective, & Research Design

If you uploaded a separate research protocol document in the 'Research Protocol' page, cite the applicable section and page numbers from that document in the answer boxes below.

- 1 *** Describe the purpose, specific aims, or objectives of this research. State the hypothesis to be tested:**
 Specific aim 1: Examine the effects nutrition + multimodal balance intervention (MMBI) on mobility and functional performance in the following outcomes:
 a. 6 minute walk (primary outcome)
 b. Other physical performance outcomes: 6MW with economy of gait, gait rite, four square step test, 8 foot up and go, short physical performance battery, grip strength, lower extremity strength
 Specific aim 2: Examine the relationship between muscle mass, strength, and functional performance using DXA and CT scans to quantify body composition.
 Specific aim 3: Examine the impact of the intervention on patient reported measures of function and disability using the Late Life Function and Disability Instrument (LLFDI).
- 2 *** Discuss the research design including but not limited to such issues as: probability of group assignment, potential for subject to be randomized to placebo group, use of control subjects, etc.:**
 All subjects will now receive MMBI and nutrition (combined intervention). Weight loss will be a covariate in the analyses.
- 3 *** Describe the relevant prior experience and gaps in current knowledge. Describe any relevant preliminary data:**

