 Seventeen older (age >70 years) adults with a history of falls were recruited for a preliminary study of our MMBI. Subjects exercised 3 times/week for 16 weeks in our gymnasium followed by a four-month long home exercise regimen (adapted from the VISION 8 program) after completion of the center-based portion of the intervention. Sixteen out of 17 individuals completed all portions of the study with > 90% adherence in the 16 who completed the study. Six of the 16 fell at least once during the 4 months of the home-based phase of the study, and an additional six subjects reported at least 1 near fall. These falls and near falls did not occur during the exercise, but rather during normal daily activities. Four-square times in those who fell were significantly slower (12.7 +6.5 seconds) than in those who did not fall (6.0 + 2.1 seconds, p < 0.01). Notably, however, the slower individuals also had the greatest improvement with the intervention. After 16 weeks of center-based exercise, MMBI scores on the functional gain assessment increased by 12% and the time to complete the four-square test decreased by 24%, with even greater improvements of 40-50% for individuals whose function was most impaired at baseline. Distance covered during the six minute walk increased by 5% (p < 0.04). Maximum weight lifted during a leg press increased demonstrating significant improvements in lower extremity strength. Importantly these improvements were maintained after the four-month home-based exercise program. The subjects in this study differ from those we propose to study as the primary enrollment criteria was a history of falls, not obesity. In addition, there was no requirement that they use walking assistive devices. Nevertheless, these findings demonstrate that our multimodal intervention can be performed safely in an at risk population and improves multiple physical performance domains.
 GEROFIT cross-sectional data

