We anticipate that some participants will have acute medical events during the study and may need to curtail or temporarily suspend the exercise intervention. When this occurs, the participant's status will be changed to 'suspended'. When medically cleared, we will perform a modified re-initiation of the training phase until the participant can re-establish exercise intensity previously performed, at which time they will resume the study at the week at which they were assigned suspended status. If an acute medical event occurs in the 2 weeks prior to the planned interim or final month outcome assessment, we will postpone the assessment until at least 6 thrice-weekly in-center training sessions can be completed at target exercise intensity. Participants who are on medical hold for more than 4 concurrent weeks will be evaluated on an individualized basis by the site PI to assess their appropriateness to return to intervention activities.

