Specific aim 2. Using DXA and CT scans, we will quantify total muscle mass and cross-sectional muscle area at numerous levels at baseline, 3, 6, 12, and 24 months. At baseline there should be a direct correlation between total muscle, ASMI, cross-sectional muscle mass and the indices of functional performance. With the exercise intervention, we expect that there will be small, but significant increases in lean muscle mass and ASMI (ANOVA). This change may be beyond the limits of detection of the DXA. Assessment of cross-sectional muscle area by CT scan may provide a more sensitive measurement of muscle mass than DXA. The relationship between muscle mass, strength, and functional performance at baseline and after the intervention will be examined. Body composition (% fat, fat-free mass, regional distribution of body fat) may change with intervention. Regression analyses will be used to determine whether the change in 6MWD, and other mobility parameters are related to the change in muscle mass (DXA, CT scan) or muscle strength (Biodex) with intervention. We will also perform multivariate modeling. It is important to dissect how much of the improvement in mobility after intervention is attributable to changes in fitness, economy of gait, and other factors such as balance, and strength. The functional measures in combination with the assessments of muscle mass by DXA will also allow us to determine the prevalence of sarcopenia using recently published NIH guidelines.

Specific Aim 3. We will examine the impact of the intervention on patient reported measures of function and disability using the LLFDI. We will compare LLFDI total scores and subscale scores using an analysis plan similar to that for aim 1. We will also examine the correlations between the self-reported measures and performance measures to provide further evidence of validity and reliability.

ID: VIEW4E02806052800
Name: v2_Sample Size and Data Analysis

Sharing of Results

1 * Describe whether results (study results or individual subject results, such as results of investigational diagnostic tests, genetic tests, or incidental findings) will be shared with subjects or others (e.g., the subject's primary care physicians) and if so, describe how it will be shared:
Results which have clinical relevance will be shared with participants, and with their permission, their primary care providers.

ID: VIEW4E02808CBD800
Name: v2_Sharing of Results

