People who respond to our advertisements will be contacted by telephone and informed about the general aspects of the study. The information we obtain from subjects during the telephone screening will be entered into the IRB approved Pepper Center Registry (H-28418). This registry is designed to collect and store information across research studies undertaken by investigators in the VA and University of Maryland. Information in the registry will be used to screen subjects for entry into this research project, as well as serve as a source of subjects for future recruitment into new IRB approved studies carried out by UMB and VA researchers. As described in the Pepper Center Registry IRB application (H-28418), the only data that will be stored in the registry will be data that has previously been approved for collection by the IRB under this IRB application. Thus, we are not requesting permission to collect new data. Only those subjects who approve having their data entered into the registry and agree to be re-contacted in the future for new studies will be entered in the registry. If at some time in the future subjects wish to have their data removed from the registry, the data will be removed. The design and procedures related to the entry of data in the registry and their protection are detailed in section F1 of H-28418, including the protection of PHI data by encryption and limiting access to the registry (i.e. by requiring a user name and password as well as access to the secured VA local area network).

- 3 * **Describe the plan to destroy the PHI collected during this study at the earliest opportunity consistent with the conduct of the research. If there is a need to retain PHI, provide a justification:**
All PHI will be retained in accordance with the Dept. of Veterans Affairs Records Control Schedule (RCS 10-1).
- 4 * **Why could the research not practicably be done without access to and use of this PHI?**
The only PHI collected was directly for the conduct of the research, whether to facilitate contact/communication with the participant (or their PCP) or to document confounding health variables. The PHI is necessary to identify individual patients and determine their potential eligibility for this study.
- 5 * **Why could the research not practicably be done without the waiver or alteration?**

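### Aim 2 relates change in walking to change in muscle or strength without naming any baseline or health adjuster, so its result should be adjusted for starting values and reported as an association

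*Combined protocol and SAP*

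**What the plan says.** Specific aim 2 (Sample Size and Data Analysis, item 2) uses regression to ask whether the changes in 6MWD and other mobility measures "are related to the change in muscle mass (DXA, CT scan) or muscle strength (Biodex) with intervention". It then adds "We will also perform multivariate modeling" and wants to know how much of the improvement is "attributable to changes in fitness, economy of gait, and other factors such as balance, and strength". The factors it lists are themselves changes over the intervention. Relationships at baseline are to be examined, but as a separate analysis and not as an adjustment in the change regression.

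The research design answer (Justification, Objective, & Research Design, item 2) gives the combined intervention to every participant and says "Weight loss will be a covariate in the analyses". No other covariate is named.

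Two other places bear on the point:
- **Starting function.** In the pilot of the balance intervention (same section, item 3): "Notably, however, the slower individuals also had the greatest improvement with the intervention". The four square step test (FSST) time fell by 24% overall, and by 40-50% in those most impaired at baseline.
- **Illness.** Study Procedures, item 1: "We anticipate that some participants will have acute medical events during the study". If the event falls in the two weeks before an assessment, that assessment is postponed.

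Separately, the Waiver/Alteration of Authorization page (item 4) says PHI is collected for the research, "whether to facilitate contact/communication with the participant (or their PCP) or to document confounding health variables".

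**The concern.** With one treated arm there is no randomised contrast behind Aim 2. Whether people who gained more muscle or strength also walked further is a comparison between people within that arm. Anything that moves both changes together will produce a slope even if muscle has no effect on walking.

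The plan points to two candidates. Those with low starting function may gain more on several measures at once. An acute illness may lower walking distance, strength and muscle together. Neither a starting value nor a marker of illness is named in the model. The multivariate step, as described, brings in further change scores that the same causes can move.

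At stake is the interpretation of Aim 2. A significant slope could be reported as improvement due to muscle or strength when it partly reflects who started low or fell ill.

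**Working it through.** **1. Sample size.** The plan enrols 60 and expects 20-25% attrition: 60 × (1 − 0.25) = 45 completers, as stated. The 45 per group also reproduces as a two-sample figure for 30 m with SD 50 m: 2 × (1.96 + 0.84)² × 50²/30² ≈ 44, or 45 with the t distribution. No power is stated for the Aim 2 regression. At n = 45 and two-sided alpha 0.05, the smallest significant correlation is |r| = 0.294, and 80% power needs r of about 0.41.

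**2. Mechanism.** Let one cause correlate a with the mobility change and b with the muscle or strength change, with no other link between them. The induced correlation is a × b. I took a = b = c (an assumption; the documents give no such values) and simulated 20,000 trials of 45 per setting.

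| c | Induced r = c² | Significant, unadjusted | Significant, adjusted for the cause |
|---|---|---|---|
| 0 | 0 | 4.9% | 4.8% |
| 0.2 | 0.04 | 5.8% | 5.0% |
| 0.3 | 0.09 | 9.0% | 5.1% |
| 0.4 | 0.16 | 18.5% | 5.0% |
| 0.5 | 0.25 | 39.0% | 5.1% |

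**3. What the pilot data say about starting function.**

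*6MWD.* The SDs before and after are 118 and 122 yards (preliminary data, GeroFit). The change is 57 ± 60 m (sample size answer). I take ± as an SD and the two places as the same veterans. The second assumption is not exact: 418 − 363 = 55 yards is about 50 m, not 57 m.
- 60 m = 65.6 yards.
- Pre-post r = (118² + 122² − 65.6²)/(2 × 118 × 122) = 0.85.
- Correlation of baseline with change = (0.851 × 122 − 118)/65.6 = −0.22.
- If the 60 were yards: pre-post r = (118² + 122² − 60²)/(2 × 118 × 122) = 0.876, and (0.876 × 122 − 118)/60 = −0.19. So it is about −0.2 either way.

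That is one side only. The other side, baseline 6MWD against change in muscle or strength, is not given. If it has the same size, the induced r is 0.22² = 0.05 and the error rate about 6%. If it is 0.4 in size, the induced r is 0.22 × 0.4 = 0.09 and the rate about 9%.

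*FSST.* The SDs are 5.0 and 4.2 s. Assuming pre-post r = 0.8, the change SD is √(5.0² + 4.2² − 2 × 0.8 × 5.0 × 4.2) = 3.01. The baseline-change correlation is (0.8 × 4.2 − 5.0)/3.01 = −0.55. Pre-post r of 0.7 or 0.9 gives nearly the same value.

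**4. Illness.** The documents give no figure for how strongly acute events move walking, muscle or strength. They do say that attrition is mainly due to medical problems unrelated to the study, and that the obese pilot veterans averaged 10 medical problems. This makes the mechanism plausible but does not size it.

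**The case against.** The strongest case against is that the plan is thin rather than wrong, and several parts of that case stand.

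- **The HIPAA phrase.** A reader might infer that the sponsor promised to adjust for health confounders and then did not. The documents do not support this. The waiver is requested for recruitment before enrolment, and the sentence after the phrase gives identification and eligibility as the reason. It is a privacy justification, not an analysis commitment.
- **Unadjusted, or only under-specified?** Weight loss is a covariate in the analyses generally, and the multivariate factors are introduced as examples. The plan therefore does not rule out other adjusters; it names none. That is enough for the point, because adjusters chosen after the results are seen give weaker protection.
- **Size.** Error rates of 18-39% need correlations of 0.4-0.5 on both sides. For 6MWD the pilot figures suggest about −0.2 on one side and nothing on the other. Part of any negative baseline-change correlation is also noise in the baseline walk, which CT, DXA and Biodex do not share and which does not confound.
- **Direction.** The pilot finding concerns FSST in people recruited for falls, whom the plan itself calls different from this population. Nothing shows that the most impaired gain most muscle or strength. Under a diet aimed at 10% weight loss, walking could improve while lean mass falls, which would bias the slope the other way.
- **Illness.** The two-week postponement removes some of the joint drop. Earlier events can still affect both changes.

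None of this removes the case for baseline adjustment. Those values are measured before any change occurs and are already collected.

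**Conclusion.** The point holds as a weakness in how Aim 2 is specified and worded. The change-on-change regression names no starting value or health variable, the design makes it observational, and attributing improvement to these changes claims more than it can show.

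The size is not known. The 6% to 39% range rests on assumed correlations of 0.2 to 0.5 on both sides with 45 completers. For 6MWD and baseline alone, the low end is the better guess. The risk may be larger for FSST, or where several causes act together, but the documents do not establish that.

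A reader might go further and conclude that illness and low starting function will be reported as a muscle effect. The documents do not support that: they show that it can happen, not that it will or in which direction. Aim 2 is not the primary analysis, so the 6MWD time-course analysis in Aim 1 is untouched.

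**What to change.** Change the Specific aim 2 text in Sample Size and Data Analysis, item 2:

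1. Model the 3-month mobility outcome on its own baseline value, baseline muscle or strength (matching the change entered), the change in muscle (CT or DXA) or strength (Biodex), age, and weight loss as already planned. Keep weight loss, since it can move both muscle and walking.
2. Report the unadjusted slope beside the adjusted one.
3. Add one sensitivity model with a yes/no term for suspension for a medical event in the first 3 months. This arises after baseline, so it belongs in a sensitivity analysis only.
4. Describe the result as an association, and drop the language of attribution.

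I would not require a count of medical problems: the screening visit promises a medical history but not a count.

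**Cost.** The terms use measurements or status the plan already records. Against a one-predictor regression, four added terms take residual degrees of freedom from 43 to 39, which widens the standard error by about √(43/39) = 1.05. With the suspension term it is √(43/38) = 1.06. The widening is greater if the covariates correlate with the change in muscle or strength. At r = 0.5 the variance inflation is 1/(1 − 0.25) = 1.33, so collinearity alone widens it by about 15%, and with the first factor by about 1.05 × 1.155 = 1.21. Outcome variance explained by baseline offsets part of this. About 45 completers will not support many more terms.

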2.1 Does the research involve the use of ionizing radiation?

Yes

2.2 Does the research involve the sampling of radioactive human materials for subsequent use in laboratory research?

If the answer to this question is wrong, a RSC submission is not required, use the Jump To menu and return to the Organization Review Requirements page to change your answer.

3 *** Confirm** - you have read the above information and understand that in addition to the IRB Protocol form, you will complete and submit the RSC Submission form :

Yes No

ID: VIEWE1AF92170C00

Name: v2_Radiation Safety Committee Review Required

Institutional Biosafety Committee Review Required

1 **NOTE:** based on your answers to questions on a previous page (see below) review by the Institutional Biosafety Committee (IBC) is required. This will involve extra steps on your (study team) part. Clicking the Continue button will result in the system creating a blank IBC Submission form for you. You will be required to fill out and submit this IBC form before you will be able to submit the Protocol form. The IBC Submission workspace and form can be reached by clicking the appropriate button on the left hand side of the Protocol submission's workspace (web page) after exiting the Protocol form.

2 **Question** - answered on IBC RSC review requirements page: Yes

3.1 Does the research involve human gene transfer? - OR - Does the research specifically apply to human studies in which induction or enhancement of an immune response to a vector-encoded microbial immunogen is the major goal, and such an immune response has been demonstrated in model systems, and the persistence of the vector-encoded immunogen is not expected? This type of research is often referred to as recombinant vaccine trials. Yes

3.2 Does the research involve: a) the exposure of human subjects to pathogenic microorganisms, or b) the potential exposure of UMB research staff to infectious materials through the sampling or processing of materials from patients with known infectious disease or from environmental surfaces?

3.3 Does the research involve the sampling of materials from persons with no known infectious disease and where the only risk to study staff is occupational exposure to bloodborne pathogens as defined by the OSHA Bloodborne Pathogen Standard?

If the answer to this question is wrong, an IBC submission is not required, use the Jump To menu or your browser's <

3 * **Confirm** - you have read the above information and understand that in addition to the IRB Protocol form, you will fill out and submit the IBC Submission form :

Yes No

ID: VIEW4E1AF91ED4C00
Name: v2_Institutional Biosafety Committee Review Required

VA-Specific Criteria

1. * **What is the relevance of this research to the mission of VA and the Veteran population that it serves*?**
This study is particularly relevant to the older veterans as the prevalence of obesity continues to rise, placing older Veterans at increased risk for disability, morbidity and mortality. Even modest improvements in physical functioning in this older population with dysmobility may significantly impact on their ability to live independently in the community and reduced ADL dependence and potentially decrease institutionalization. This research directly benefits Veterans as it may lead to new and more effective interventions that could reduce disability, reduce fall risk, and reduce injury-related hospitalization and death. This nutritional and multimodal exercise intervention is readily exportable to the community and with minimal resources, could be widely implemented at other VAs as part of clinical care as an enhancement to MOVE!. Thus, the proposed interventions are likely to have real world impact on Veterans and their health.

2. * **Describe who will be enrolled in this study:**
 - Non-veterans will be enrolled in this study
 - Only veterans will be enrolled in this study
 - Veterans and Non-veterans will be enrolled in this study

- 2.1. * **If non-veterans will be enrolled in this study, provide a description of non-veterans who will be enrolled (For example: community members, family members/caretakers of Veterans, clinicians/caregivers to Veterans, etc.):**
not applicable

- 2.2. **If non-veterans will be enrolled in this study, provide a substantive justification** for the enrollment of non-veterans in this research:**

- 2.3. * **If this is a VA-funded study, was the use of non-veterans discussed within your merit award proposal?**
 - Yes
 - No
 - N/A

*

http://www.va.gov/about_va/mission.asp

VA Mission Statement

To fulfill President Lincoln's promise "To care for him who shall have borne the battle, and for his widow, and his orphan" by serving and honoring the men and women who are America's Veterans.

VA Core Values

VA's five core values underscore the obligations inherent in VA's mission: Integrity, Commitment, Advocacy, Respect, and Excellence. The core values define "who we are," our culture, and how we care for Veterans and eligible beneficiaries. Our values are more than just words – they affect outcomes in our daily interactions with Veterans and eligible beneficiaries and with each other. Taking the first letter of each word—Integrity, Commitment, Advocacy, Respect, Excellence—creates a powerful acronym, "I CARE," that reminds each VA employee of the importance of their role in this Department. These core values come together as five promises we make as individuals and as an organization to those we serve.

Integrity: Act with high moral principle. Adhere to the highest professional standards. Maintain the trust and confidence of all with whom I engage.

Commitment: Work diligently to serve Veterans and other beneficiaries. Be driven by an earnest belief in VA's mission. Fulfill my individual responsibilities and organizational responsibilities.

Advocacy: Be truly Veteran-centric by identifying, fully considering, and appropriately advancing the interests of Veterans and other beneficiaries.

Respect: Treat all those I serve and with whom I work with dignity and respect. Show respect to earn it.

Excellence: Strive for the highest quality and continuous improvement. Be thoughtful and decisive in leadership, accountable for my actions, willing to admit mistakes, and rigorous in correcting them.

**

a. Non-Veterans may be entered into a VA-approved research study that involves VA outpatient or VA hospital treatment (38 CFR 17.45, 17.92), but only when there are insufficient Veteran patients suitable for the study. The investigator must justify including non-Veterans and the IRB must review the justification and provide specific approval for recruitment of non-Veterans.

b. Non-Veterans may be recruited for studies that will generally benefit Veterans and their well-being but would not include Veterans as subjects. Examples include surveys of VA providers, studies involving Veterans' family members, or studies including active duty military personnel. Although active duty military personnel are not considered Veterans, they should be included in VA studies whenever appropriate.

e. Non-Veterans may not be entered into VA studies simply because a non-Veteran population is easily accessible to the investigator.

[VHA Handbook 1200.05 §24]

VA Prohibited Research

- 1 * Is the research planned emergency research in subjects from whom consent can not be prospectively obtained?
 Yes No

- 2 * Does the study involve children **AND** is greater than minimal risk?
 Yes No

- 3 * Will recruitment phone calls involve asking veterans for their Social Security numbers?
 Yes No

ID: VIEW4E1C8AF03A400
Name: V2_VA Prohibited Research

Additional VA

- 1 * For data that is combined, which site is the "Data Coordinating Center"?
Data is not combined
- 2 If VA data will be combined with non-VA data, describe when and how this will occur and where the combined data will be stored.
n/a
- 3 If the VAMHCS is the Local Coordinating Center holding the "combined data", how is the data collected? (This answer may overlap with Research Related Procedures. If so, please refer to that section.)
n/a
- 4 If the VAMHCS is the Local Coordinating Center holding the "combined data", how is the data received and combined with the data from the other non-VA institution(s)?
n/a

ID: VIEW8D5931EAC5B1E6E
Name: v2_Additional VA

VA Maryland Health Care System Review Required

1 **Note:** Based on the answers provided in your submission, this protocol qualifies as a VA study and therefore requires VA-specific reviews to ensure that all VA regulatory requirements are met. The VAMHCS Research & Development Committee (RDC) review is included in these VA-specific reviews and RDC approval is required prior to engaging in any research activities. **Importantly, you must submit this protocol to the VAMHCS RDC for review within 60 days of IRB approval. Please see below for a summary of required VA-specific review steps.**

****Before you initiate any of the following VA-specific review steps, please contact [name] ([contact]), VAMHCS Research Protections Officer (RPO), to ensure full compliance with VA requirements.**

1. Ensure that you have already created a new project shell in IRBNet and that the title matches the title for this IRB application. Before drafting the IRB submission, the PI **should have completed Package 1 – ACOS New Project Review Form** found in the VAMHCS IRBNet library (log in to IRBNet first and then click on link), gotten it signed by the PI's VA Service Chief, and submitted it to the Research Service as a single document package within this project shell in IRBNet.
2. After you have received ACOS sign-off, you may submit your protocol application in CICERO. The application will be routed to designated reviewers including [name], VAMHCS RPO. She will conduct a VA Administrative Pre-Review and the results will be communicated to the study team through the CICERO platform and may include suggested edits to the application and consent/HIPAA form(s). The study team will be responsible for implementing these edits in CICERO.
3. While the VA Specialty Review is being conducted in CICERO, complete the Information System Security Officer (ISSO) review form and email to [name] so she can prepare her request for that additional, required review. You can find the form used for ISSO review in the VAMHCS IRBNet library (log in to IRBNet first and then click on link): **RDC – Information Security Officer Review Form.pdf**.
4. After all suggested edits have been made in the CICERO application and consents/HIPAA by the study team, [name] will then send for VAMHCS ISSO and Privacy Officer (PO) review and the study team will be copied on these correspondences. (Please Note: [name] will prepare PO review form).
5. Once you receive approval from ISSO and PO, [name] will finalize her review and send the CICERO application on to the next UMB HRPO-required reviewing body.
6. You will then create another new package in your IRBNet project shell (i.e., the same project shell you already created for ACOS review) to submit the protocol documents for Subcommittee on Research Safety (SRS) review. You can find all applicable submission forms in the VAMHCS IRBNet library (log in to IRBNet first and then click on link). Please use this form within the library as a submission guide: **IRBNet Admin Review Checklist – Used only as a guide for submitters – Does not have to be uploaded**.
7. After your protocol has been approved by the IRB, you'll create a third, new package in your IRBNet project shell (i.e., the same project shell you already created for ACOS review and used to submit documents for SRS review) to submit the protocol documents required for Research and Development Committee (RDC) review. You can find all applicable submission forms in the VAMHCS IRBNet library (log in to IRBNet first and then click on link). Please use this form within the library as a submission guide: **IRBNet Admin Review Checklist – Used only as a guide for submitters – Does not have to be uploaded**.
8. Only after you have been approved by RDC, you may initiate study activities.

2 **Questions answered on 'Organizational Review Requirements' page:**

The research will be conducted by VA Investigators including PIs, Co-PIs, and Site Investigators on VA time (serving on compensated, WOC, or IPA appointments): **Yes**

The research will utilize VA resources (e.g. equipment, funds, medical records, databases, tissues, etc.): **Yes**

The research will be conducted on VA property, including space leased to and used by VA: **Yes**

Questions answered on 'VA Prohibited Research' page:

The research is planned emergency research in subjects from whom consent can not be prospectively obtained: **No**

The study involves fetuses: **No**

The study involves in vitro fertilization: **No**

The research involves work with embryonic stem cells: **No**

The study involves children AND is greater than minimal risk: **No**

Recruitment phone calls involve asking veterans for their Social Security numbers: **No**

If the answers to these questions are wrong, use the Jump To menu to return to the 'Organization Review Requirements' page to change your answers.

3 *** Confirm** - You have read the above information and understand that in addition to this IRB application form (CICERO), you are required to send a submission to the VAMHCS R&D Committee **within 60 days of receiving IRB approval**.

Yes No

Summary of Required Reviews (other than IRB)

1 Additional Committee Reviews - Based on your responses to the previous questions, you have identified the following additional reviews. To complete or view these additional committees' forms, click on the links below or exit this application and click on the appropriate button on left side of this submission's webpage.

Name of Related Submission

RSC: (RSC-00001163)

IBC: Multimodal Exercise and Weight Loss in Older Veterans with Dysmobility (HP-00069566)

Workspace

SmartForm

Workspace

SmartForm

2 Required Department and Specialty Reviews - Based on the PI's organization (department, division, etc.) affiliation and answers to previous questions (use of Cancer Center, etc.), the organizations listed below are required to review this application. These reviews are conducted online and no additional forms or steps by the study team are required.

Name of Organization

Med Gerontology

Review Status

Complete

ID: VIEW4E1C8D9AE4000
Name: v2_Summary of Required Reviews (other than IRB)

Additional Documents

1 Upload all additional documents here:

Name	Created	Modified Date
HP69566 UMB COVID Risk Statement Action.docx(0.01)	3/11/2021 2:49 PM	3/11/2021 2:49 PM
COVID 19 Preparedness and Response Plan 1.20.21 track changes version.docx(0.01)	3/10/2021 11:03 AM	3/10/2021 11:03 AM
track changes consent form 02272021.docx(0.01)	3/10/2021 10:23 AM	3/10/2021 10:23 AM
grecc infection control plan january 2021(0.01)	2/28/2021 10:24 AM	2/28/2021 10:24 AM
letter to subjects 02272021(0.01)	2/28/2021 10:18 AM	2/28/2021 10:18 AM
tracked consent form (0.01)	3/12/2020 11:49 AM	3/12/2020 11:49 AM
[name] real ssn back.pdf(0.01)	10/3/2019 2:59 PM	10/3/2019 2:59 PM
[name] real ssn front.pdf(0.01)	10/3/2019 2:59 PM	10/3/2019 2:59 PM
[name] waiver of HIPAA front (0.01)	10/3/2019 2:58 PM	10/3/2019 2:58 PM
[name] waiver of HIPAA back.pdf(0.01)	10/3/2019 2:58 PM	10/3/2019 2:58 PM
Qtug brochure(0.01)	9/24/2019 10:33 AM	9/24/2019 10:33 AM
Track changes consent form 9.16.19(0.01)	9/16/2019 4:00 PM	9/16/2019 4:00 PM
RISE update contact info letter(0.01)	11/8/2018 1:23 PM	11/8/2018 1:23 PM
[name] CITI Training(0.02)	9/21/2017 8:31 AM	9/21/2017 8:33 AM
[name] Citi Training(0.01)	7/7/2017 8:52 AM	7/7/2017 8:52 AM
response to reviewers 07202016(0.01)	7/20/2016 2:41 PM	7/20/2016 2:41 PM
ISOPO Checklist Signed by ISO and PO.pdf(0.01)	6/14/2016 12:53 PM	6/14/2016 12:53 PM
ISO PO Checklist signed.pdf(0.01)	6/1/2016 9:42 AM	6/1/2016 9:42 AM
[name] VA merit grant(0.01)	5/23/2016 10:54 AM	5/23/2016 10:54 AM

ID: VIEW4E0962513A000
Name: v2_Additional Documents

Final Page of Application

You have reached the final page of this application. It is recommended that you click on the "Hide/Show Errors" link on the upper or lower breadcrumb row of this page. The "Hide/Show Errors" will do a search of your application, and highlight areas that are required or need to be completed prior to submitting.

By submitting this application, you are electronically routing the protocol for departmental scientific review and all other necessary reviews. According to information you have provided, this application will be routed to the following Departments for review prior to being forwarded to the IRB for review. These reviews are conducted online and no additional forms or steps by the study team are required.

Name of Organization

Review Status

Med Gerontology

Complete

